 - We hypothesize that awake caudal catheter technique when compared with single-dose caudal injection and general anesthesia will be of greater benefit to preterm infants via the following primary quantifiable measures: reduction in the time to return of baseline respiratory function, reduction in the number of apneic episodes (defined as cessation of breathing by a premature infant that lasts for more than 20 seconds and/or is accompanied by hypoxia or bradycardia), and a reduction in bradycardic events (heart rate <90).
 - We hypothesize that secondary measures will be of greater benefit to preterm infants as well with decreased days to hospital discharge, decreased number of post-operative narcotic use days, decreased mechanical ventilation days, and decreased time to full oral feeds.

Such results are expected to advance the field of pediatric anesthesiology and pediatric surgery which will impact clinical practice by changing the peri-operative management of high risk NICU patients.

6. Research Plan:

Inclusion and Exclusion Criteria

Patients included in the study are preterm infants in the NICU less than 50 weeks post gestational age born at less than 37 weeks gestational age. Patients will be within 1 week of meeting NICU discharge criteria with or without supplemental oxygen prior to surgical scheduling for inguinal hernia repair. Males and females will be included in this study, but there is a known higher incidence of male inguinal hernias in the literature, approximately 6:1.

Patients undergoing other invasive procedures including but not limited to gastrostomy tube placement, tracheostomy, and/or laser eye treatments will be excluded. Any patient with a medical condition that would prevent a regional anesthetic from being performed (i.e. bleeding diathesis, vertebral anomalies, spinal cord injury prior to surgery) and any contradictions to the prescribed medications in the protocol will be excluded.

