Currently, there are no published articles in the literature to help generate a level of data which can be used to determine the power analysis. We would want a power of 80% and a significance level of 0.05 for the study and after the first 10 patients are enrolled we can calculate a reliable sample size. Based on previous studies conducted in a prospective, randomized fashion we approximate approximately 20 patients in each arm though this is only speculation until the first ten patients are enrolled (Oghazian MB, 2015) (Rakhshani A, 2015) (Mathur NB, 2015). A review from 1/1/2014 – 12/31/14 of NICU patients undergoing inguinal hernia repair at Wolfson was performed and totaled 21. We estimate approximately 80% study inclusion and 20% exclusion. [name], a Nemours statistician will perform all statistical analysis of the study and has indicated the following will be used in the analysis. Demographic and baseline data will be summarized by treatment groups, namely general anesthesia and caudal catheter groups. Quantitative variables will be summarized by mean/SE or median/interquartile range (IQ), whichever appropriate. Categorical variables will be summarized by frequencies and percentages. A chi-square or Fisher exact analysis will be used to compare the general anesthesia group and the caudal catheter infusion group in the primary outcome, which is time to return to baseline respiratory function. A Cox hazard model ratio will compare the hazard risk between the two groups and a log rank test will calculate the median time to return to baseline function. In addition, a Cox proportional hazards model will be used to compare the risk of failure between two groups. A poisson regression analysis will compare the number of bradycardic events, apneic events, catheter complications, and number of post-operative narcotic use days between the general anesthesia group and the caudal catheter infusion group. A logistic regression model will be used to compare the proportion of successful surgical completion between two groups. We estimate the study will run two years for adequate patient accrual. Data will be input by the research nurse and sent for analysis to the statistician for periodic review every three months. Primary outcomes that will be analyzed in the statistical analysis are: time to return of baseline respiratory function, successful surgical completion, catheter complications, number of apneic episodes (defined as cessation of breathing by a premature infant that lasts for more than 20 seconds and/or is accompanied by hypoxia or bradycardia), and bradycardic events (heart rate <90). Secondary outcomes are: days to hospital discharge, number of post-operative narcotic use days, operative time, mechanical ventilation days, and time to full oral feeds.

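### The test attached to the primary time outcome is chi-square or Fisher with no time point stated, and nothing says whether it or the planned Cox and log-rank analysis decides.

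*Combined protocol and SAP*

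**What the plan says.** All of the analysis wording is in Section 6 (Research Plan), Statistical Analysis.

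- The test attached to the outcome: "A chi-square or Fisher exact analysis will be used to compare the general anesthesia group and the caudal catheter infusion group". The same sentence goes on to identify what is compared: "in the primary outcome, which is time to return to baseline respiratory function".
- The next sentence begins: "A Cox hazard model ratio will compare the hazard risk between the two groups". Its second half gives the log-rank test this role: "a log rank test will calculate the median time to return to baseline function". A separate Cox model is then assigned to the risk of failure, so this first one is reasonably read as belonging to the recovery time.
- The hypothesis, in the second aim of Section 5: a "reduction in the time to return of baseline respiratory function".
- Sample size: about 20 per arm, "though this is only speculation until the first ten patients are enrolled", with a desired power of 80% and a significance level of 0.05. Sidedness is not stated.
- Data handling: data are "sent for analysis to the statistician for periodic review every three months".

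The documents give no cut-off, fixed assessment time or categories for this outcome, and no order among its analyses. The 30 minutes in the blinding text of Section 6 is an extubation and transport rule; it is not linked to this outcome.

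**The concern.** A chi-square or Fisher test needs a two-by-two table, here the number of infants back at baseline by some stated time. Without that time there is no table. The analysis tied by name to the primary outcome is therefore undefined, and as written it does not address whether recovery is faster.

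The Cox and log-rank sentence does address speed. But two different comparisons of one outcome, unranked and one lacking its cut-off, do not fix in advance what counts as a positive result. In a trial of about 40 infants these tests can easily disagree. At stake are the power of the primary comparison and, if the choice were left until data had been seen, its false-positive rate.

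The log-rank wording is a smaller slip: that test compares two curves and gives a p-value; a median comes from an estimator such as Kaplan-Meier.

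**Working it through.** **1. Inputs.** From the plan: about 20 per arm, 1:1 allocation, significance level 0.05, desired power 80%. The plan's 20 cannot be reproduced, because no effect size, rate or hazard ratio is given. Its accrual figures (21 eligible repairs a year; "We estimate approximately 80% study inclusion and 20% exclusion"; two years) give 21 × 0.80 × 2 = 33.6 infants, about 17 per arm. Power is therefore shown at 20 per arm, with [17; 30] in brackets. Assumed, not in the documents: two-sided tests, exponential times, no censoring, and the effect sizes below.

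**2. Illustrative hazard ratio.** By the Schoenfeld formula, 40 events give 80% power at HR = exp[(1.960 + 0.842) / √(40 × 0.25)] = exp(0.886) = 2.43.

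**3. Power under proportional hazards, HR 2.43.** Cut at the control median, the proportions back at baseline are 50% and 1 − 0.5^2.43 = 81%. Fisher and chi-square are by exact binomial enumeration, log-rank by simulation.

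| Test | Power at 20 [17; 30] per arm |
|---|---|
| Log-rank | 76% [69; 91] |
| Chi-square, uncorrected | 58% [50; 74] |
| Fisher | 46% [36; 65] |

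The cut-off matters as well: with 25%, 50%, 75% or 90% of controls back at baseline, simulated Fisher power at 20 per arm is 28%, 45%, 37% and 4%.

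**4. Power if the effect is confined to NICU arrival** (later times alike in both arms; Fisher and chi-square applied at arrival).

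| Test | 40% v 80% at baseline on arrival | 50% v 90% |
|---|---|---|
| Log-rank | 48% [43; 60] | 62% [57; 73] |
| Chi-square, uncorrected | 75% [70; 91] | 84% [75; 95] |
| Fisher | 65% [56; 85] | 74% [63; 91] |

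The order reverses. At 20 per arm the rank-sum test has 72% and 81% in these two cases, and 64% under HR 2.43. An early-weighted Peto-Peto test has about 72% and 81% if its weights are taken just before each event time, but only about 61% and 71% with the modified weights.

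**5. False-positive rate with no true effect, 20 per arm.** Log-rank alone rejects about 6% (large-sample version). One cut-off fixed in advance at the control median rejects 2.0% with Fisher and about 4.3% with chi-square. If the best of the four cut-offs in step 3 were picked after seeing data:

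| Version of the two-by-two test | Best of four cut-offs | Best of four, or log-rank |
|---|---|---|
| Fisher throughout | about 7% | about 10% |
| Chi-square if all expected counts are at least 5, otherwise Fisher | about 12% | about 13% to 14% |
| Uncorrected chi-square throughout | about 15% | about 16% to 17% |

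**The case against.** The strongest reply is that the right method is already there. The plan lists a Cox hazard ratio and a log-rank test for this outcome and assigns the analysis to a statistician. A reader might infer that the trial has no valid analysis of its primary outcome. The documents do not support that; what is missing is a ranking and a cut-off.

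A reader might also infer that the three-monthly reviews will be used to pick the favourable test. The plan does not say that those reviews compare the arms, or that they precede the choice of test. It only fails to rule this out.

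The size of the harm also needs care. A threefold false-positive rate requires a search over several cut-offs with uncorrected chi-square even where cells are sparse: with 90% of controls back at baseline, about two per arm are expected not to be. Read in the usual way, with Fisher for small counts, the inflation is smaller. Log-rank or Fisher at the median cut alone rejects 6.9%, barely above log-rank by itself. Part of the 30-point power gap between log-rank and Fisher reflects test size, about 6% against 2%; the 18-point gap to chi-square (76 − 58) is the fairer comparison.

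All of this stands as a limit on the size of the point. It does not supply the missing time point or say which result decides.

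**Conclusion.** The point holds in a limited form. The test named for the primary outcome cannot be run as written, and the plan does not say whether it or the Cox and log-rank analysis decides. This rests on the text alone.

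The figures illustrate why it matters. The choice of test moves power by roughly 10 to 30 points at about 20 per arm, and which test does better depends on the shape of the effect, which the documents do not give. It would therefore be wrong to infer that a two-by-two test is always the weaker option here. The false-positive range of about 10% to 17% applies only if test and cut-off were chosen after seeing data.

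The log-rank wording is an editorial slip and carries no weight of its own. The point concerns this outcome only and does not deal with the five outcomes listed as primary without ranking.

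**What to change.** Before any comparative data are reviewed, including at the three-monthly reviews, replace the chi-square/Fisher sentence and the one after it with wording such as:

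> The deciding between-group test for the time until respiratory function is back at baseline is the two-sided log-rank test at the 0.05 level. The effect measure is the Cox hazard ratio with its 95% confidence interval. Medians are taken from Kaplan-Meier curves. The proportion back at baseline at one pre-stated time is compared by chi-square or Fisher exact test as a supporting analysis.

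The definition of baseline, time origin, assessment times and censoring rule should be written down alongside.

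**Cost.** A few sentences; no new patients, visits or data. The downside is power if the effect is confined to arrival: log-rank then gives up about 21 to 28 points to a chi-square test at that time (75 − 48 = 27 and 84 − 62 = 22 in the two cases above, with some simulation error). If the investigators expect that pattern, they should instead name one deciding test suited to it: a rank test such as the rank-sum, or an early-weighted test with its weights stated, since the weights determine how much power is recovered. Under proportional hazards that choice costs about 11 to 12 points (log-rank 76%, against 65% for Peto-Peto with weights just before each event and 64% for rank-sum).

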It is well established that preterm inguinal hernias discovered in the NICU pose a significant surgical risk due to the associated co-morbid conditions that accompany these patients. There have been studies that have established that elective outpatient repair of inguinal hernias found in the NICU can be safely performed. However, due to the low associated risk of incarceration and subsequent bowel loss many institutions are reluctant to treat this way and practice is widely variable (Sulkowski JP, 2015). The most common practice in NICUs across the country is to wait until the patient is ready for discharge from the NICU and to perform inguinal hernia repair prior to discharge (Crankson SJ, 2015). This allows for the patient to undergo significant growth in the NICU without increasing the risk of incarceration. Currently and historically this operation is performed under general anesthesia, which requires the preterm neonate to be intubated during the procedure and depending on their respiratory status, sometimes afterward. A recent review of current practices in regards to inguinal hernia repair in the United States demonstrated that 70% of repairs are performed with general anesthesia (Wiener ES, 1996). Due to the known risk of apnea and bradycardia in the preterm infant, alternatives to general anesthesia for inguinal hernia repair has been hotly debated in the surgical, anesthetic, and neonatology literature. General anesthesia with single-shot caudal injection is an established practice with demonstrated safety. A study utilized this technique where 91 out of 126 patients safely underwent general anesthesia and caudal injection (Murphy, 2008). Recent studies suggest that low gestational and postconceptional age, low birth weight, anemia, and complicated past medical history affect respiratory complication rates, particularly apnea in formerly premature infants undergoing elective inguinal hernia repair (Ozdemir T, 2013). Spinal anesthesia is currently the most common anesthetic procedure used in the surgical treatment of preterm inguinal hernias after general anesthesia, although spinal anesthesia is not currently in wide surgical practice due to its high failure rate that is up to 28% in some studies (López T, 2012). Spinal anesthesia in the preterm infant has been found to decrease apneic events as well as decrease post-operative prolonged mechanical ventilation, although the latter is disputed in the literature (G, 2003).

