In the caudal infusion group, Precedex 0.5 mg/kg IV will be administered for sedation over 10 minutes and maintained with an infusion of 0.7 mg/kg/h. Under ultrasound guidance a 20 gauge angio-catheter will be placed into the caudal space and secured to the skin with a tegaderm. A low volume extension catheter will be connected to the angio-catheter and bupivacaine .3% + 1:200,000 epinephrine (dose 3mg/kg) will be administered via the catheter. An additional dose of 1mg/kg will be administered at 1 hour post initial dosing time to extend the duration of the caudal. Intravenous caffeine and rectal Tylenol will be administered for apnea prevention and additional pain control. If patient agitation is noted during the operation, an additional bolus of Precedex 0.5 mg/kg will be administered. If agitation persists, pain, and/or respiratory distress are noted during the operation, general anesthesia will be induced with propofol 3 mg/kg and rocuronium 0.6 mg/kg followed by endotracheal intubation. The angio-catheter will be removed at the end of the surgical procedure. Pain management in the NICU will be the following: mild to moderate pain based on a FLACC scale will receive rectal or oral Tylenol, while moderate-severe pain will receive IV morphine 0.05mg/kg.

Blinding of the study will occur on the day of surgery by the anesthesiologists. Prior to a patient arrival to operating room, the anesthesiologist will randomly draw an envelope from a folder that will allocate group assignment (this precludes bias while discussing patient care with parents and getting consent). It is estimated that we will need approximately 20 patients in each group. 10 envelopes at a time will be placed in the folder, 5 will be in the awake caudal catheter group and 5 will be in the general anesthesia and single-dose caudal group. This will keep the numbers equal when going forward with the study.

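### No baseline adjustment is prespecified and randomization is not stratified, although the plan names factors that affect respiratory outcome; fixing two covariates in advance is a cheap improvement

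*Combined protocol and SAP*

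**What the plan says.** All references are to the combined protocol and SAP.

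- **Section 6, Statistical Analysis.** On time to return to baseline respiratory function: "A Cox hazard model ratio will compare the hazard risk between the two groups". Poisson regression for event counts and logistic regression for surgical completion are likewise described only as comparisons of the two groups. No covariate is named in any model. Baseline data have a descriptive use: "Demographic and baseline data will be summarized by treatment groups".
- **Section 6, randomization paragraph.** Envelopes go into the folder ten at a time: "5 will be in the awake caudal catheter group and 5 will be in the general anesthesia and single-dose caudal group". No stratification factor is given.
- **Section 4, Background.** Recent studies are cited as suggesting that "low gestational and postconceptional age, low birth weight, anemia, and complicated past medical history affect respiratory complication rates", with apnea singled out. Section 5 adds bronchopulmonary dysplasia, of varying severity, as the most common risk factor under general anesthesia.
- **Section 6, Inclusion and Exclusion Criteria.** Infants are eligible "with or without supplemental oxygen".

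**The concern.** The plan identifies characteristics that it believes drive respiratory outcome, admits infants who differ on them, and then uses them in neither allocation nor analysis. At about 40 infants this has two consequences. One arm can by chance hold noticeably more infants on oxygen or of lower maturity, with no prespecified way to allow for it. And in a Cox model, leaving out a covariate that truly predicts the event time pulls the treatment hazard ratio towards 1 and lowers power.

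Silence also leaves room for covariates to be chosen after the data are seen, and data are to go to the statistician every three months. A choice fixed in advance closes that route.

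**Working it through.** **1. The plan's own figure.** The plan states "We would want a power of 80% and a significance level of 0.05 for the study" and "we approximate approximately 20 patients in each arm though this is only speculation until the first ten patients are enrolled". No effect size supports this; the plan says "there are no published articles in the literature to help generate a level of data which can be used to determine the power analysis". So 20 per arm cannot be reproduced, only back-solved. If all 40 infants return to baseline (assumed; 40 events) and the test is two-sided (assumed), Schoenfeld's formula gives the hazard ratio (HR) detectable with 80% power:

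HR = exp[2 × (1.960 + 0.842) / √40] = exp(0.886) = 2.43.

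A value of 2.4 is used below. It is an assumption and not a claim about this treatment.

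**2. Chance imbalance.** Let the number on oxygen in each arm be Binomial(20, p). A gap of 4 infants is 4/20 = 20 percentage points. The prevalence p is not in the documents.

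| Assumed prevalence p | P(gap of at least 4 infants) |
|---|---|
| 10% | 6% |
| 20% | 16% |
| 40% | 26% |

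**3. Cox power with and without adjustment.** Simulation of 3,000 trials per row: 20 per arm, exponential times, no censoring, treatment HR 2.4, 40% on oxygen, two-sided Wald test at 0.05. The covariates are oxygen (yes/no) and age (per SD). All covariate effects are assumed.

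| Oxygen HR / age HR per SD | Unadjusted | Adjusted | Change (points) |
|---|---|---|---|
| 1 / 1 (not prognostic) | 74% | 72% | -2 |
| 0.8 / 1.1 | 74% | 73.5% | about 0 |
| 0.7 / 1.2 | 69% | 72% | +3 |
| 0.5 / 1.3 | 62% | 71% | +9 |
| 0.4 / 1.5 | 55% | 72% | +17 |
| 0.3 / 1.7 | 49% | 71% | +22 |

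The Monte Carlo standard error of one power figure is about √(0.7 × 0.3 / 3000) = 0.8 points; independent repeats agreed to within about 3 points.

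**4. Type I error.** With no treatment effect, the adjusted Wald test rejected in about 6-7% of trials and the unadjusted test in about 5-6%. Part of the gain in step 3 therefore comes from a liberal test. With both tests calibrated to 5%, the change runs from about -4 to +18 points. These ends are rougher, because the cut-offs are themselves simulated.

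**5. What is estimated.** The Cox hazard ratio is non-collapsible. In the last row of step 3 the median estimate was 1.87 unadjusted and 2.49 adjusted. The two models estimate different quantities even under perfect balance.

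**6. Which models can carry covariates.** Section 4 cites a caudal failure rate below 5%, so at most about 20 × 0.05 = 1 failure is expected among 20 caudal infants. The completion and failure models cannot support adjustment. For the Poisson models the documents give no event rate, and no gain has been computed.

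**The case against.** The case against is substantial.

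- **Validity.** Under 1:1 randomization the unadjusted test holds its error rate, and that rate already allows for chance imbalance. This stands. A reader might infer that the unadjusted estimate is biased or the test invalid; the design does not support that.
- **Size.** A reader might infer that the plan gives up a known amount of power, such as 6 to 23 points. It does not follow. Such figures depend wholly on assumed covariate effects, and an oxygen hazard ratio of 0.5 is not a weak effect. The honest range includes zero and a small loss.
- **Strength of the predictors.** The Background says that the factors affect respiratory complications. It does not call them strong, and it does not address time to return to baseline. Supplemental oxygen is not in its list; it appears as an eligibility allowance. If baseline means the infant's own pre-operative status, oxygen may already be partly built into the endpoint. Entry within a week of meeting discharge criteria may also narrow the variation. All of this stands as a reason for caution about the size of the gain.
- **Deciding test.** The plan also assigns a chi-square or Fisher test to the primary outcome, and 20 per arm is provisional. The power figures therefore apply only if the Cox model decides.
- **Silence.** The plan does not exclude adjustment; it specifies none. That is correct, and it is why the remedy is prespecification.

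None of this removes the benefit of fixing a short covariate list in advance. If the covariates are useless the expected loss is a few points; if they matter the gain may be much larger.

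**Conclusion.** The point holds as a cheap improvement and not as an error that invalidates the analysis. The plan specifies neither adjustment nor stratification, while naming factors that it believes affect respiratory outcome. The benefit is precision and protection from chance imbalance.

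The Cox power change is about -2 to +22 points, or about -4 to +18 with calibrated tests. It is conditional on 20 per arm, HR 2.4, 40% on oxygen, no censoring and the covariate effects tabulated; none of these effects comes from the documents. For the Poisson models the argument rests on the Background's statement about apnea alone, and no size is claimed. The completion and failure models are outside the recommendation.

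**What to change.** In section 6, Statistical Analysis, before the first infant is enrolled:

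1. Name postconceptional age at surgery (continuous) and pre-operative supplemental oxygen (yes/no, recorded before the envelope is drawn) as the only two covariates. Use them in the Cox model for time to return to baseline respiratory function and in the Poisson models for apneic and bradycardic events.
2. Leave the completion and failure models unadjusted, because events will be too few.
3. Report the unadjusted results as supportive, and state that the adjusted hazard ratio is conditional on the covariates.
4. Do not rely on the Wald test for the adjusted Cox model. A likelihood-ratio test is the simpler replacement, but in a check under the same assumptions it was about as liberal as the Wald test. A permutation test, re-drawing assignments within the sets of ten among randomized infants, is therefore preferable.

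**Cost.** A few sentences of SAP wording, no extra infants and no change to care. Both items should be available before surgery, since eligibility already refers to age and oxygen. The downsides are a slight loss of power if the covariates are not prognostic, an adjusted hazard ratio that differs in meaning from the unadjusted one, and the need to keep the list at two.

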This will be a prospective, blinded, randomized controlled clinical trial. When the NICU staff and surgeon decide that inguinal hernia repair is warranted, a research representative will approach the family for research consent. [name] and [name] will provide the anesthesia for both groups and will obtain anesthesia consent on the day of surgery. The general anesthesia and single-shot caudal group will be induced with intravenous (IV) propofol 3mg/kg and rocuronium 0.6mg/kg and intubated. Caffeine 15mg/kg and rectal Tylenol 30mg/kg will then be given for apnea prevention and pain control. Caudal will be performed under ultrasound guidance with bupivacaine 0.25% + 1:200,000 epinephrine (total dose 2.5mg/kg) prior to start of the surgery. At the conclusion of the operation, neuromuscular blockade will be reversed with neostigmine and glycopyrrolate. The patient will be extubated once criteria are met. If the patient is unable to extubate within 20-30 minutes, they will be transferred to the NICU intubated with assisted ventilation. The general anesthesia group will not receive narcotics for pain management intra-operatively due to the increased risk of apnea and bradycardia. Since the study is attempting to answer whether the act of exposure to general anesthesia changes the likelihood of apnea and bradycardia, we need to maintain the same approach to pain management in both groups. No Precedex will be given in the general anesthesia group. Pain management in the NICU will be the following: mild to moderate pain based on a FLACC scale will receive rectal or oral Tylenol, while moderate-severe pain will receive IV morphine 0.05mg/kg.

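### Narcotic-use days are assigned to a Poisson model with no provision for dispersion, so the test's error rate is uncontrolled in a direction the documents do not settle; a rank test avoids this

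*Combined protocol and SAP*

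**What the plan says.** All references are to the combined protocol and SAP.

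- **Method (Section 6, Statistical Analysis).** "A poisson regression analysis will compare the number of bradycardic events, apneic events, catheter complications, and number of post-operative narcotic use days" between the two arms. The comparison at issue here is the last in that list, the "number of post-operative narcotic use days between the general anesthesia group and the caudal catheter infusion group". No dispersion check, robust standard error, quasi-Poisson scale or exact alternative is mentioned.
- **Role.** The same section lists the variable among five secondary outcomes: "Secondary outcomes are: days to hospital discharge, number of post-operative narcotic use days, operative time, mechanical ventilation days, and time to full oral feeds". Section 5, Aim 2, hypothesises a "decreased number of post-operative narcotic use days", so an inferential comparison is intended.
- **Pain regimen (Section 6).** Both arms have the same NICU ladder: Tylenol for lesser pain, while "moderate-severe pain will receive IV morphine 0.05mg/kg". No maximum number of narcotic days, expected duration or share of infants needing morphine is given.
- **Size.** "We would want a power of 80% and a significance level of 0.05 for the study", and "we approximate approximately 20 patients in each arm though this is only speculation until the first ten patients are enrolled". Envelopes are filled 1:1 in sets of ten: "5 will be in the awake caudal catheter group and 5 will be in the general anesthesia and single-dose caudal group".

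**The concern.** A narcotic-use day is a yes or no for each calendar day. The infant's total is therefore not a count of independent events, and nothing ties its variance to its mean. The Poisson standard error depends on that tie.

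- If most totals are 0 or 1 and morphine use is common, the variance is below the mean. The model's standard error is too large, and a real reduction is harder to detect.
- If a few infants have long courses, the variance is above the mean. The standard error is too small, and false positives follow.

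The plan would apply the test without knowing which case it is in. What is at stake is whether the p-value and interval for one Aim 2 comparison can be believed.

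**Working it through.** **The plan's own figure.** The 20 per arm cannot be reproduced, because no effect size, rate or SD is stated. It corresponds to 80% power for a standardised difference of about 0.89 at two-sided 0.05: 2 × (1.960 + 0.842)² / 0.89² = 19.8. The documents give no power or dispersion for narcotic days.

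**Inputs.** From the documents: about 20 per arm, 1:1, alpha 0.05 (sidedness not stated; two-sided assumed). Every distribution of days below is an assumption, varied to show the range.

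**Formula.** Let φ = variance/mean. If both arms share one distribution, Poisson model SE / true SE = 1/√φ. For 0/1 totals with probability p of a narcotic day, φ = p(1−p)/p = 1−p.

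**Rejection under the null.** Simulated with 100,000 runs, 20 per arm, Wald test of the log rate ratio at nominal 5%:

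| Share of infants at 0 / 1 / 2 / 5 days (%) | Mean | φ | Model SE / true SE | Rejects |
|---|---|---|---|---|
| 90 / 10 / 0 / 0 | 0.10 | 0.90 | 1.05 | 0.03% |
| 80 / 20 / 0 / 0 | 0.20 | 0.80 | 1.12 | 0.5% |
| 50 / 50 / 0 / 0 | 0.50 | 0.50 | 1.41 | 0.5% |
| 40 / 50 / 10 / 0 | 0.70 | 0.59 | 1.31 | 0.9% |
| 30 / 50 / 20 / 0 | 0.90 | 0.54 | 1.36 | 0.8% |
| 70 / 20 / 10 / 0 | 0.40 | 1.10 | 0.95 | 4.7% |
| 80 / 10 / 10 / 0 | 0.30 | 1.37 | 0.86 | 5.6% |
| 50 / 35 / 10 / 5 | 0.80 | 1.70 | 0.77 | 12% |
| 70 / 15 / 10 / 5 | 0.60 | 2.40 | 0.65 | 19% |

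Worked example, last row: mean = 0.15 + 2(0.10) + 5(0.05) = 0.60; mean square = 0.15 + 4(0.10) + 25(0.05) = 1.80; variance = 1.80 − 0.36 = 1.44; φ = 1.44/0.60 = 2.4; 1/√2.4 = 0.65. In the first two rows the very low rejection comes largely from sparse totals, since the standard error is only 5% to 12% too large.

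In the null cases simulated for it, including the long-tail ones, a Wilcoxon rank-sum test rejected about 4% to 5% of the time. Sandwich standard errors gave about 8% to 9% with the long tail.

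**Unequal arms, 0/1 days.** The SE ratio is √[(1/p₁ + 1/p₂) / ((1−p₁)/p₁ + (1−p₂)/p₂)]:

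- 10% v 5%: √(30/28) = 1.04
- 20% v 10%: √(15/13) = 1.07
- 30% v 15%: √(10/8) = 1.12
- 60% v 30%: √(5/3) = 1.29
- 80% v 40%: 1.46

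**Power, 20 per arm (simulated).**

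| Assumed shares (%) | Poisson | Alternative |
|---|---|---|
| 0/1/2 days: 20/60/20 v 50/45/5 | 30% | Wilcoxon about 60% |
| 0/1 days: any use 60 v 30 | 20% | Wilcoxon 44%; Fisher 35% |
| 0/1/2 days: 20/50/30 v 70/25/5 | 86% | robust SE 90%; quasi-Poisson 92% |
| 0/1/2 days: 70/20/10 v 85/10/5 | 16% | robust SE 13%; quasi-Poisson 12% |

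Check of the first row: the means are 1.00 and 0.55, with φ = 0.40 and 0.632. Model SE = √[(1/1.00 + 1/0.55)/20] = 0.375. True SE = √[(0.40/1.00 + 0.632/0.55)/20] = 0.278. The log ratio is ln(1/0.55) = 0.598. Poisson power ≈ Φ[(0.598 − 1.96 × 0.375)/0.278] = Φ(−0.49) ≈ 31%, close to the simulated 30%.

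**The case against.** A reader might infer something stronger: that the regimen makes nearly all totals 0, 1 or 2, that the Poisson standard error is therefore 30% to 45% too large, and that a real narcotic-sparing effect would usually be missed. The documents do not support this.

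- **No cap on days.** Section 6 sets no limit on narcotic use. It foresees escalation of narcotics and transfer to the NICU while intubated, so courses of several days are possible. Being within a week of discharge criteria is an eligibility condition before surgery and does not limit narcotic days afterwards.
- **The size depends on the input.** An excess of 30% to 45% needs φ of 0.59 to 0.48. With 0/1 totals, that means 41% to 52% of infants have exactly one narcotic day. The nearest figure in the documents is Section 7's rate of inadequate pain control, below 5%. It concerns the caudal technique and is not a morphine rate, but it does not point to common use.
- **The direction can reverse.** This happens with 5% of infants at five days, and even within 0/1/2 (80/10/10 gives a ratio of 0.86).
- **Missed effects are partly a matter of sample size.** At 60% v 30%, Fisher's test (35%) and the Wilcoxon test (44%) also miss more often than not.

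All of this stands, as does the point that the outcome is secondary. None of it defends the Poisson test: an unknown direction is a reason to choose a method whose validity does not depend on dispersion.

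**Conclusion.** The point holds in a conditional form. The plan names a Poisson test for narcotic-use days and makes no provision for dispersion. At 20 per arm, the nominal 5% test can reject under 1% of the time, with loss of power, or about 12% to 19% of the time. Which applies depends on a distribution that the documents do not give. The low end assumes mostly 0/1 totals with about half of infants using morphine. The high end assumes about 5% of infants with five-day courses. With rare use, the standard error is only about 4% to 12% too large. Neither a general loss of power nor a general excess of false positives can be claimed. The consequence is confined to one secondary comparison under Aim 2.

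**What to change.** Take narcotic-use days out of the Poisson sentence. Compare them between arms by a Wilcoxon rank-sum test with tie correction, or by a permutation test, and name this as the main analysis of the outcome. Alongside it, report the proportion of infants with any post-operative narcotic, compared by Fisher's exact test with a confidence interval for the difference. Sandwich standard errors on the Poisson model are a weaker fallback, given their type I error of about 8% to 9% with a long tail. A negative binomial model does not help if the variance is below the mean.

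Replacing days with cumulative morphine dose would change the endpoint. That is a matter of preference and is not needed to resolve this point.

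The cost is one or two sentences in the Statistical Analysis section, with no new data. The downside is that the result is no longer a rate ratio; the difference in proportions supplies an interpretable effect size.
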